## PROTOCOL: Neuroimaging During Pure Oxygen Breathing

Consented study participants will be asked to come to the Case Western Reserve University Magnetic Resonance (MR) Facility located within University Hospitals on [name] at a scheduled date/time. Data collection will involve 1 visit lasting approximately 3-4 hours in length.

### PROCEDURE:

1. Confirmation of signed informed consent & repeat MRI screening to ensure subject safety
2. Obtain focused neurological history and physical examination
3. Obtain baseline vital signs
4. Apply HD-EEG head cap on scalp, apply EEG gel, and program EEG acquisition software, check impedances
5. Obtain 5 minutes of baseline EEG recording
6. While the participant is breathing room air and EEG is being recorded, administer baseline neurocognitive assessments
7. Obtain baseline arterial blood sample for blood gas and venous blood sample for inflammatory markers. Perform Allen test for collateral circulation prior to obtaining arterial blood sample. Apply pressure over the artery for 5-10 minutes after the blood sample is obtained to minimize bleeding
8. Obtain baseline exhaled breath sample
9. Transfer participant to MRI scanning room. Final MRI safety check
10. Apply MRI-compatible respiratory monitoring sensors, pulse oximeter probe, nasal cannula, face mask
11. While the participant is breathing room air, MRI scan and simultaneous EEG recording begins
12. Continuously monitor heart and respiratory rate, oxygenation during scanning session
13. After baseline MR scans are acquired, scanning and EEG recording continues and oxygen administration is begun
14. Following 30 minutes of 100% oxygen administration, MRI scan ends. Arterial blood gas sample and exhaled breath sample are obtained while oxygen administration and EEG recording continues. Perform Allen test for collateral circulation prior to obtaining arterial blood sample. Apply pressure over the artery for 5-10 minutes after the blood sample is obtained to minimize bleeding
15. While continuing 100% oxygen breathing and EEG recording, repeat neurocognitive assessments
16. 100% oxygen breathing discontinued. Room air breathing begins
17. The participant is observed and vital signs are assessed for 30 minutes during room air breathing. Arterial puncture site is assessed for hemostasis. Participant is assisted to remove EEG gel
18. Participant is contacted within 1 week to assess for development of any adverse events

#### STATISTICAL ANALYSIS PLAN:

General statistical approaches: Sample size estimation and power analyses were based on a minimum statistical power of  $\geq 0.80$  at a two-tailed significance of 0.05. Physiologic measures were continuous in nature and frequency analyses with normality plots providing information of data distributions.

Descriptive statistics include the mean, standard error of the mean (SEM), and range. Independent samples t-tests were utilized to compare males and females, incorporating the Levene test for homogeneity of variance. Paired t-tests were used to compare physiologic measures in 21% FiO2 versus 100% FiO2.

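### Does describing the data by mean, SEM and range, with no interval for the paired oxygen effect, call for a change to the SAP?

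*Combined protocol and SAP*

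**What the plan says.** The SAP is two short paragraphs under the heading STATISTICAL ANALYSIS PLAN. On summaries it says: "Descriptive statistics include the mean, standard error of the mean (SEM), and range". It does not say whether these are computed by oxygen condition, by sex or on the within-person difference.

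The next sentence is the sex comparison: "Independent samples t-tests were utilized to compare males and females, incorporating the Levene test for homogeneity of variance". The oxygen comparison follows: "Paired t-tests were used to compare physiologic measures in 21% FiO", with 100% as the other condition.

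The pairing comes from the PROCEDURE section. EEG, neurocognitive tests, arterial gas, exhaled breath and MRI are obtained on room air (steps 5 to 8 and 11) and again on oxygen (steps 13 to 15) in the same visit; step 13 reads "After baseline MR scans are acquired, scanning and EEG recording continues and oxygen administration is begun".

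The design targets are power of at least 0.80 "at a two-tailed significance of 0.05". No sample size, effect size, SD or within-person correlation is given. No SD or confidence interval is named as an output, and the only plots mentioned are those for checking normality.

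**The concern.** Two features of the descriptive list look wrong for this design.

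- **Spread.** The SEM measures the precision of a mean, not the variation between people. It shrinks as participants are added, so it is an odd choice as a descriptive statistic.
- **The paired contrast.** If the SEM is reported for each oxygen condition, it contains between-person variance that the paired t-test removes. A reader who judged the oxygen effect from two condition SEMs would get the wrong precision. With a positive correlation, combining them as if independent gives an SE that is too wide.

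The oxygen contrast is the SAP's only comparison of exposures, yet the plan names a test for it and no estimate with an interval. For a measure that does not reach significance, the reader would want to know whether the result is a precise null or merely imprecise. A p-value alone does not show that.

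**Working it through.** **Inputs.** From the SAP: paired t-test, two-sided 0.05, power at least 0.80. Assumed, because the documents give no values: equal SDs of 1 in the two conditions, within-person correlation rho from 0 to 0.9, n of 10, 20 or 32, and a mean difference of 0.5 SD. The plan has no sample size or precision figure to reproduce.

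**Step 1: condition SEM against the SE of the paired difference.** With equal SDs, SE(difference) = SEM x sqrt(2(1 - rho)). Combining two SEMs as if independent gives SEM x sqrt(2), which is 1/sqrt(1 - rho) times the correct value.

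| rho | SE(difference) / SEM | Independent SE / correct SE |
|---|---|---|
| 0 | 1.414 | 1.000 |
| 0.3 | 1.183 | 1.195 |
| 0.5 | 1.000 | 1.414 |
| 0.7 | 0.775 | 1.826 |
| 0.8 | 0.632 | 2.236 |
| 0.9 | 0.447 | 3.162 |

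The principle is right. A single condition SEM is too small for the contrast below rho = 0.5 and too large above it, so the direction of that mismatch is unknown without rho. The independent combination is too wide for any positive rho.

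**Step 2: what a misreading would cost.** With n = 20, each SEM is 1/sqrt(20) = 0.224.

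| rho | SE(difference) | 95% CI for the mean difference | Paired p | p from two SEMs as if independent |
|---|---|---|---|---|
| 0 | 0.316 | 0.5 +/- 0.662 | 0.130 | 0.122 |
| 0.5 | 0.224 | 0.5 +/- 0.468 | 0.038 | 0.122 |
| 0.8 | 0.141 | 0.5 +/- 0.296 | 0.002 | 0.122 |
| 0.9 | 0.100 | 0.5 +/- 0.209 | 0.0001 | 0.122 |

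At rho = 0.8 the half-width is 0.452 for n = 10 and 0.228 for n = 32, with paired p of 0.034 and 0.0001. The last column is a calculation the plan does not make. The SAP uses the paired test, so the paired p is the one that would be reported.

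**Step 3: does a missing interval change any conclusion?** The 95% CI and the paired t-test share one SE and one t quantile, so the interval excludes zero exactly when p is below 0.05. At rho = 0.5 it runs from 0.5 - 0.468 = 0.032 to 0.968 (p = 0.038). At rho = 0 it runs from 0.5 - 0.662 = -0.162 to 1.162 (p = 0.130). Printing the interval adds information about size but alters no test.

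**Step 4: can the precision be obtained without rho?** With complete pairs, the mean within-person difference equals the difference of the two means, and t = difference / SE(difference). At n = 20 and rho = 0.8, t = 0.5/0.1414 = 3.54. Working backwards, 0.5/3.54 = 0.141, and the half-width is 2.093 x 0.1414 = 0.296, where 2.093 is the 0.975 t quantile on 19 degrees of freedom. An exact p with n gives the same t. For spread, SD = SEM x sqrt(n) = 0.224 x 4.47 = 1.00, and the range is listed as well.

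**Step 5: the sex comparison.** For independent groups, the unpooled SE of the difference is sqrt(SEM_males^2 + SEM_females^2). For the comparison that directly follows the descriptive sentence, group SEMs are therefore a usable summary.

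**The case for a change.** The best case for a change is that a plan should name its main estimate and not rely on software output or a reader's back-calculation. The recovery in Step 4 needs complete pairs and a reported t or exact p with n, and the SAP promises neither. It also works least well where the interval matters most: when the difference and t are both near zero, rounding makes their ratio unstable. The document gives no sample size, so precision cannot be anticipated from the plan either. The remedy would cost one sentence and no new data.

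Most of this stands as good reporting practice. It is true that no SD, paired difference or interval is named, and that the SEM is a poor descriptor of spread. What does not stand is the step from there to a fault in the analysis. The text does not tie the SEM to each oxygen condition and mentions no error bars, so a clash between plotted bars and paired p-values is conjecture. The list is introduced as what the descriptives include, which does not make it exhaustive. The rounding difficulty affects an outside reader, not the analyst, who holds the individual data and must compute the mean difference and its SE to obtain t.

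**Conclusion.** No change follows. The statistical principle is correct, and at an assumed correlation of 0.8 an SE built from two condition SEMs as if independent would be 2.24 times too wide. But the plan does not build that SE. It specifies a paired t-test, which matches the design, and its type I error and power do not depend on which descriptives are tabulated. Following the plan as written gives the same tests, p-values and conclusions as a version that named the SD and the interval.

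What is left is a gap that an analyst would normally fill from paired t-test output, together with a preference between SD and SEM. The figures rest on assumed values of rho, n and the mean difference and on equal SDs in the two conditions, none of which the documents supply. The conclusion does not depend on those values. It would be weaker only if results were published with condition SEMs and thresholded p-values alone, and nothing in the plan says that they will be.

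### The male–female t-test carries a Levene check with no stated rule; for roughly normal data, Welch without the check holds 5% better when the sexes differ clearly in both number and variance

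*Combined protocol and SAP*

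**What the plan says.** The Statistical Analysis Plan section works to a "minimum statistical power of $\geq 0.80$ at a two-tailed significance of 0.05". It names two tests. For sex: "Independent samples t-tests were utilized to compare males and females, incorporating the Levene test for homogeneity of variance". For the oxygen effect: "Paired t-tests were used to compare physiologic measures in 21" percent against 100 percent FiO2. On distributions it says: "Physiologic measures were continuous in nature and frequency analyses with normality plots providing information of data distributions".

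It does not say which t-test follows a significant or a non-significant Levene result, which version of Levene is used, or at what threshold. Welch's test is not mentioned. No total sample size, number of males and females, or SD by sex is given. The section is written in the past tense, so some of these comparisons may already have been run.

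**The concern.** The pooled t-test assumes equal variances in males and females. A Levene check is usually added to protect that assumption: if it is significant, use the unequal-variance test; otherwise pool. In small groups Levene has little power, so the pooled test is often kept when the variances really differ. If the groups are also unequal in size, the pooled standard error is then wrong. It is too small when the smaller group is more variable (too many false positives) and too large when the larger group is (a test that is too strict).

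If Levene is only reported and the pooled test is always used, there is no protection and the departure is larger. Either way, a sex difference could be reported against a nominal 5% that is not the real error rate. Welch's test needs no preliminary check, so the screen adds a step without a clear benefit.

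**Working it through.** **Inputs.** From the SAP: two-sided 5%, continuous measures, independent-samples t-test with Levene. Not in the documents, so assumed: group sizes, SD ratios of 1.5 and 2, normal data, and the rule that Levene p < 0.05 leads to Welch and otherwise to the pooled test (mean-centred Levene). The SAP gives no sample size or effect size, so it has no figure of its own to reproduce.

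**Why both imbalances are needed.** The true variance of the mean difference is s1²/n1 + s2²/n2. The pooled test estimates, on average, {[(n1−1)s1² + (n2−1)s2²]/(n1+n2−2)} × (1/n1 + 1/n2).

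- 10 v 20, SDs 2 and 1: true 4/10 + 1/20 = 0.450; pooled (9×4 + 19×1)/28 × 0.15 = 1.964 × 0.15 = 0.295. SE ratio √(0.295/0.450) = 0.81, about 19% too small.
- 10 v 20, SDs 1 and 2: true 1/10 + 4/20 = 0.300; pooled (9×1 + 19×4)/28 × 0.15 = 3.036 × 0.15 = 0.455. SE ratio √(0.455/0.300) = 1.23, about 23% too large.
- Equal n: both expressions equal (s1² + s2²)/n. Equal SDs: both equal s²(1/n1 + 1/n2). There is no distortion of the SE in either case.

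**Type I error by simulation** (200,000 normal data sets per row; Monte Carlo SE about 0.05 points). Entries are pooled / Levene-screened / Welch, in %.

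| Split | SD ratio | Smaller group more variable | Larger group more variable |
|---|---|---|---|
| 8 v 12 | 1.5 | 7.1 / 6.5 / 5.1 | 3.7 / 4.0 / 4.9 |
| 8 v 12 | 2 | 8.7 / 7.0 / 5.2 | 3.1 / 3.9 / 4.9 |
| 7 v 13 | 1.5 | 8.1 / 7.3 / 5.1 | 3.0 / 3.5 / 4.8 |
| 7 v 13 | 2 | 10.8 / 8.2 / 5.3 | 2.2 / 3.3 / 4.8 |
| 12 v 18 | 1.5 | 7.0 / 6.2 / 5.0 | 3.6 / 4.1 / 4.9 |
| 12 v 18 | 2 | 8.6 / 6.2 / 5.0 | 3.0 / 4.2 / 5.0 |
| 10 v 20 | 1.5 | 8.6 / 7.3 / 5.1 | 2.8 / 3.7 / 5.0 |
| 10 v 20 | 2 | 11.4 / 7.4 / 5.1 | 2.0 / 3.8 / 5.0 |

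Levene detects an SD ratio of 1.5 in only 15–20% of trials of 20 people and 21–28% of trials of 30. For a ratio of 2 the figures are 32–44% and 50–62%.

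**Where the effect fades.** The screened test gives 4.3–5.9% at 13 v 17, 4.7–5.4% at 15 v 17 and 5.0–5.1% at 15 v 15. With equal SDs it gives 4.9–5.2% at every split tried. At 20 v 40 and SD ratio 3, Levene almost always rejects and the error returns to 5.0%.

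**Skewed data** (equal means, smaller group more variable; screened / Welch):

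- Exponential: 10 v 20 at ratio 1.5, 6.5% / 7.5%; 12 v 18 at ratio 2, 8.3% / 7.8%.
- Lognormal, log-SD 0.8: 10 v 20 at ratio 2, 9.8% / 9.7%.
- Lognormal, log-SD 0.5: 10 v 20 at ratio 2, 8.6% / 7.0%.

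**Power cost of Welch with equal SDs** (screened v Welch), at a 0.8 SD difference: 15 v 15, 56.2% v 56.0%; 12 v 18, 54.3% v 53.6%; 10 v 20, 51.2% v 49.6%; 6 v 14, a loss of 2.5 points. At 6 v 14 with a 1.45 SD difference: 79.7% v 75.3%, a loss of 4.4 points (4.6 in a repeat run).

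**The case against.** Screening with Levene is conventional and openly stated, and the SAP never says that Levene selects the test. On that view the gap is an unwritten rule, and one sentence stating the rule would close it. This is fair as to the text. But either plausible rule leaves type I error off 5% under the conditions above, so writing the rule down would disclose the problem without removing it.

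The assumed splits and SD ratios are the reviewer's. Near balance the screened test moves by less than a point, and nothing in the documents shows that the groups were small or unequal. This stands in full and limits what can be claimed.

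A reader might infer that Welch guarantees 5%. It does so only for roughly normal data. With clear skew it can reach 7–10%, and at an SD ratio of 1.5 it can be about a point worse than the screen. The SAP itself plans normality plots, so distribution shape is a real question for these measures. This also stands, and the fix has to allow for it.

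Welch is also not always nearly free. Its cost is largest in small, very unequal groups, which is where the screen does worst.

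**Conclusion.** The point holds as a modest, conditional improvement. For roughly normal data with SD ratios of 1.5–2 and 20–30 people split 60:40 to 2:1, the screened test runs at about 6–8% or about 3–4%, depending on which group is more variable. An unscreened pooled test runs at about 7–11% or 2–4%, and Welch at about 4.8–5.3%. All of this rests on assumed group sizes and SDs.

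Three stronger readings are not supported. A reader might infer that this trial's sex p-values are wrong; without numbers and SDs per sex, neither the size nor the direction of any error can be known. A reader might infer that the 21% v 100% FiO2 results are in doubt; those use paired tests, which the Levene step does not touch. A reader might take this as a criticism of how sex differences in oxygen response are tested; the documents state no such claim. The point concerns any male–female t-test, and nothing in the documents makes that comparison primary.

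**What to change.** Replace the Levene step with one sentence: male–female comparisons use Welch's t-test without a preliminary variance test, reported as the difference with its 95% CI and with the number and SD in each sex. The last item lets a reader judge how far unequal numbers and variances could matter.

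Add that where the planned normality plots show clear skew, the measure is first put on a suitable scale (such as log), because Welch alone does not restore 5% there. A log-scale result compares geometric means, and the report should say so.

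Cost: no new data. With equal variances, Welch gives up about 0–2 points of power at splits up to 2:1 and about 2.5–4.6 points at 6 v 14. Any sex comparison already completed would need rerunning on the same data.

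### Do the paired t-tests on unnamed physiologic measures need a named primary outcome and multiplicity control?

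*Combined protocol and SAP*

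**What the plan says.** The Statistical Analysis Plan is two short paragraphs. On sample size it says "Sample size estimation and power analyses were based on a minimum statistical power of" at least 0.80 "at a two-tailed significance of 0.05". It gives no outcome, effect size, standard deviation or number of participants. It describes the physiologic measures only as continuous.

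Two families of tests are planned. For the sexes, "Independent samples t-tests were utilized to compare males and females", with a Levene test. For oxygen, "Paired t-tests were used to compare physiologic measures in 21" per cent against 100 per cent inspired oxygen. Neither family has a list of measures, a primary outcome, a count of tests or a multiplicity rule.

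The Procedure shows what could enter the paired tests:

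- **Neurocognition.** Step 6: "While the participant is breathing room air and EEG is being recorded, administer baseline neurocognitive assessments"; repeated on oxygen at step 15.
- **Arterial blood gas.** Step 7: "Obtain baseline arterial blood sample for blood gas and venous blood sample for inflammatory markers"; the arterial sample is repeated at step 14. The venous inflammatory sample is listed at baseline only and cannot be paired.
- **Exhaled breath.** Step 8: "Obtain baseline exhaled breath sample"; repeated at step 14.
- **MRI and EEG.** Step 11: "While the participant is breathing room air, MRI scan and simultaneous EEG recording begins"; both continue once oxygen starts at step 13.
- **Heart rate, respiratory rate and oxygenation.** Monitored throughout scanning (step 12).

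**The concern.** The paired sentence speaks of measures in the plural, several kinds of data exist under both conditions, and the only significance level in the document is 0.05. If each measure is tested at that level and none is ranked first, 0.05 is the error rate of a single test. The chance of at least one false finding across the study is larger. A reader could then be shown one nominally significant result as an effect of oxygen without knowing how many comparisons lay behind it.

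The power statement adds to the doubt. A target of 80% at 0.05 normally belongs to one particular comparison, and the plan does not say which.

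**Working it through.** **Reproducing the plan's own figure.** This is not possible. There is no sample size, effect size, standard deviation or test count to recompute. What follows illustrates the scale of the issue.

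**Inputs.** Two-sided alpha of 0.05 and power of 0.80 come from the Statistical Analysis Plan. The following are assumed: k = 3 to 6 paired tests, one variable for each kind of data, arterial oxygen and oximetry left out because they only confirm the exposure, every null hypothesis true, and a common correlation of 0, 0.3, 0.5 or 0.9 between test statistics.

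**Unadjusted error.** With independent tests the chance of at least one false positive is 1 − 0.95^k. With common correlation ρ it is 1 − ∫ φ(u) [Φ((c − u√ρ)/√(1−ρ)) − Φ((−c − u√ρ)/√(1−ρ))]^k du, with c = 1.960.

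| k | ρ = 0 | 0.3 | 0.5 | 0.9 |
|---|---|---|---|---|
| 3 | 14.3% | 13.6% | 12.5% | 8.4% |
| 4 | 18.5% | 17.4% | 15.6% | 9.4% |
| 5 | 22.6% | 20.9% | 18.3% | 10.2% |
| 6 | 26.5% | 24.1% | 20.7% | 10.8% |

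**Error with one primary at 0.05 and Holm on the rest.** A false positive needs either the primary at 0.05 or the smallest secondary P value at or below 0.05/(k−1).

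- Six tests, independent: 1 − 0.95 × 0.99^5 = 9.7%. At correlation 0.3 and 0.5: 9.1% and 8.2%.
- Three tests, independent: 1 − 0.95 × 0.975^2 = 9.7%. At correlation 0.3 and 0.5: 9.3% and 8.7%.

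The reduction therefore runs from 12.5 − 8.7 = 3.8 percentage points (three tests, correlation 0.5) to 26.5 − 9.7 = 16.8 points (six independent tests). It is obtained only if the primary is chosen before results are seen.

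**Price in power.** Take a secondary measure with exactly 80% power at 0.05.

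- Five secondaries, first Holm step 0.05/5 = 0.010. Normal approximation: Φ(1.960 + 0.842 − 2.576) = Φ(0.226) = 59%. With the paired t distribution: about 50% for 10 participants (standardised effect 0.996) and 55% for 20 (0.660).
- Two secondaries, first step 0.05/2 = 0.025. Normal approximation: Φ(1.960 + 0.842 − 2.241) = Φ(0.561) = 71%. With the paired t distribution: 68% for 10 participants and 70% for 20.

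The numbers of participants are assumed. With five secondaries the loss at the first step is 21 to 30 points.

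**The case for a change.** The strongest case for a change is this. A plan that invokes 80% power at 0.05 implies that some comparison was powered, and naming it would take a sentence. If the work is exploratory, the plan could say so, and it does not. The assumed three to six tests may also be too few: the EEG is high-density and MRI can yield many variables. With 10 or 20 independent tests the unadjusted figure would be 1 − 0.95^10 = 40.1% or 1 − 0.95^20 = 64.2%.

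Part of this stands. The measures are neither named nor ranked, and the same is true of the comparison of males and females. A report that showed only the significant results would mislead.

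The rest does not carry through to a change, for four reasons.

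- The Procedure lists what is collected, not what is tested. The monitoring at step 12 may be for safety, neurocognition may not count as physiologic, and the SAP mentions no test by EEG channel or MRI region. The larger test counts are conjecture.
- The power sentence cannot be assumed to rest on a single oxygen comparison. It refers to power analyses in the plural, and a comparison by sex is planned too. Making the powered oxygen comparison primary could mean choosing one that never existed.
- Holm across the kinds of data is one acceptable scheme among several. Reporting every comparison with its confidence interval, as exploratory, is another.
- The SAP describes its tests as already done. If they are, a primary named now would be post hoc, and none of the error reductions above would be achieved.

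**Conclusion.** No change to the plan follows. The omission is genuine, but it is a gap in written detail that the analysts fill when they list the measures they compared. Only the sponsor can supply that list, since the SAP and Procedure do not contain it; the opening page was not available for this check.

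As to size, the unadjusted chance of at least one false oxygen effect is 12.5% to 26.5% for three to six null tests at correlations from 0.5 down to 0, and 8.4% to 10.8% at correlation 0.9. Those figures rest on assumed test counts, assumed correlations and one variable for each kind of data. They show a general property of multiple testing and do not measure an error in this plan.

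Formal correction would reduce that chance to about 8% to 10% at correlations of 0 to 0.5, at a cost of up to 30 points of power for a secondary measure. In a single-visit, within-person physiology study whose SAP and Procedure state no confirmatory objective, experienced statisticians could reasonably choose either course. The conclusion would differ if a document showed that one result was to be claimed as confirmatory at a study-wide 5% level. Nothing in the SAP or the Procedure does.
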